### 16.3. Primary end-points

~~Table 16-2~~~~Table 10-2~~ is an outline of the analysis of the performance of the AP device primary end-points some of which are more qualitative than quantitative. All measures will be performed using CGM values. Below the table, the listed questions will be used as a guidance to perform the qualitative review of the AP device.

**Table 16-2: Primary end-point measures**

Measure	Description
Review qualitatively profile of predictions and actual CGM values	Ability of the zone-MPC and HMS algorithms to predict fall and rise of glucose value beyond the zone [80-140] mg/dL (1)
Review qualitatively actual data of insulin pump delivery	Capacity of the control algorithm to command the pump to increase or decrease the insulin pump to keep the subject within the zone [80-140] mg/dL (2)
Review all warning events of HMS. Review of events that required outside intervention but was not raised by HMS.	Capacity of the HMS in raising appropriate warnings and alarms to require outside intervention to prevent hypoglycemia (3)
% of time within zone [80-140] mg/dL except 5 hours post-prandial and during exercise and 3 hours post-exercise	Measures ability of AP device to maintain glucose level within a safe zone and to return to safe zone following unannounced meals and exercises.
% of time within zone [80-140] mg/dL during night between 12:00 am and 7:00 am	Measures ability of AP device to maintain glucose level with a safe zone during the night and prevent hypoglycemia.
% of time within zone [70-180] mg/dL 5 hours after unannounced evening meal, and breakfast	Measures ability of AP device to react to small meal and to prevent glucose level from dangerous excursions.
% of time within zone [70-150] mg/dL during the 30 min exercise	Measures ability of AP device to maintain safe glucose level during 30 minutes of non-strenuous exercise
% of time within zone [70-150] mg/dL during the 3 hours following exercise	Measures ability of AP device to address exercise and to prevent glucose level from dangerous excursions

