	
Following the successful screening and informed consent process:
 
During the week prior to the CRC visit, the subject will review glucose control and insulin pump settings with study staff, with goal to aim for optimal glucose control. (Subject's basal rate settings are used for insulin delivery during closed-loop mode when glucose is predicted to be within determined glucose zones, and insulin to carbohydrate ratios are used in study test meal calculations).
 
Two to three days prior to the CRC visit, the subject will attend an outpatient visit for the insertion, by study staff, of two CGM sensors, as well as to receive training and instructions on how to care for the CGM. The CGM will be in blinded mode during the 2-3 days as an outpatient. The Bayer Contour® NEXT EZ blood glucose meter will be used for all CGM calibrations.
 
Two to three days after this sensor insertion visit, the subject will return to the CRC for approximately 25-28 hours, during which the evaluation of the AP device will occur. The CGM will be unblinded.
 
On the first day of the CRC visit, the subject will arrive at approximately 4:00 pm. If the subject's blood glucose is greater than 250 mg/dL at arrival to the clinic, the study will be rescheduled. All times are +/- 30 minutes.
 

• Closed-loop will start at approximately 4:30 pm.

• A small evening meal (~50g CHO) will be given at approximately 6:30 pm without announcing it to the device, i.e. without providing any information to the device. The meal will be preceded by administering a single dose of Technosphere® Insulin (10U) using the Gen2C inhaler.

• Night time will be from approximately 12:00 am to 7:00 am.

• Another small meal (~50 g CHO) will be given for breakfast at approximately 7:00 am. The meal will be preceded by administering a single dose of Technosphere® Insulin (10U) using the Gen2C inhaler.

• At 11:00 am, the subject will be given a snack (~16 g CHO) and start exercise.

• The subject will exercise for 30 minutes at 50% of his/her target heart rate.

• At approximately 2:00 pm, the subject will be given another snack (~16 g CHO).

• At around 4:30 pm, i.e. 24 hrs after starting, closed-loop will end.

 
During the CRC visit, all diabetes care and use of the AP device will be the responsibility of the investigator. The insulin brand (subcutaneous) used during the CRC session will be the same as the brand used by the subject. Technosphere® Insulin will be delivered using the 10U Gen2C cartridge per the Investigator's Brochure manufacturer's instructions. A detailed plan for diabetes monitoring and for responding to hypoglycemia and hyperglycemia will be in place as described by this protocol. Subject will be monitored closely by trained study staff during the entire CRC visit. A physician will be present at all time.
 
The CGM will be calibrated as required by the manufacturer, as well as approximately 30 minutes before each meal and before bedtime. Additional calibrations may also be performed as required.
 
Blood glucose will be monitored by YSI at least every 30 minutes. More frequent monitoring may be performed as defined in the protocol to ensure the safety of the patient.
 
Each time a YSI measurement will be taken, a finger stick measurement using the CONTOUR® NEXT EZ blood glucose monitoring system will be performed to

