  - The subject will check in at Sansum Diabetes Research Institute at approximately 4:00 pm and have the insulin pump of the study inserted by the physician. Both CGM receivers will be unblinded during the CRC visit. The subject's own insulin pump will be disconnected. An intravenous catheter will be inserted for blood samples and for IV administration of glucose, if necessary.
  - The closed-loop will start at approximately 4:30 pm.
  - Approximately 2 hours later, the subject will be given a small unannounced meal consisting of 50 g of CHO.
  - The subject will sleep overnight at the center, while connected to the AP device.
  - At 7:00 am, another unannounced meal (breakfast) consisting of 50 g of CHO will be given.
  - At 11:00 am, a small snack of approximately 16 g CHO if YSI value is <120 mg/dL and the subject will start exercising for approximately 30 min at 50% of the his/her predicted heart rate reserve.
  - Approximately 3 hours after end of exercise, a small snack of 16 g CHO will be given.
  - Closed-loop will be stopped at approximately 4:30 pm, 24 hours after starting.
  - The subject will return to using his/her own insulin pump and CGM (open loop), once stable, the subject will be discharged from the CRC. Blood ketones will be measured. The subject will be discharged only if:
    - Blood glucose is greater than 90 mg/dL for 1 hour

- Blood glucose is less than 180 mg/dL with ketones less than 0.6 mmol/L.
- The study personnel will contact the subject in person on site or by phone approximately 24 hours after the discharge as a follow-up.

The *responsiveness factor* used in the control algorithm is decided for each patient based on the results from the previous subject. The default nominal setting of the *responsiveness factor* will be *Q/R* ratio of 1:15. Changes of the *responsiveness factor* will be decided upon clinical results from each subject in evaluating the frequency and severity of hypoglycemia and the hyperglycemia. A subject will only be studied for 1 setting of the *responsiveness factor*. The decision of changing the *responsiveness factor* setting will be made by the investigator to ensure the overall safety of the study.

Figure 10-2 is a graphical representation of the study design and the expected glucose level profile during the 24-hour closed loop.

[figure not shown]

Figure 10-2: Clinical Study Design

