### **10.4.4. Exercising**

Approximately 5 hours after the breakfast (11:00 am  $\pm 30$  min), the subject will undergo exercise for 30 minutes ( $\pm 5$  minutes) at 50% of his /

her predicted heart rate reserve (HRR). The subject will be monitored for approximately 6 hours following the end of the exercise segment or until his/her blood glucose has stabilized within the [80-140] mg/dL range. During and for 3 hours after exercise, the subject will be monitored to verify that his/her glucose level returns and remains within the range of [70-150] mg/dL.

If the subject's blood level is >270 mg/dL the subject will not go through the exercising segment of the trial, but will continue the closed-loop until the end of the 24-hour trial. Subjects whose glucose level is below 120 mg/dL at (11:00 ± 30 min) will be given 16 g CHO tablets and will not start exercise until glucose is greater than 120 mg/dL.

Exercise will be done by cycling on a recumbent stationary bicycle or by walking on a treadmill for 30 minutes (15 minutes of exercise, 5-minute break, followed by 15 additional minutes of exercise) at approximately 50% predicted heart rate reserve (HRR). HRR is calculated using the following formulas. The calculation is different for men and women.

HRR: Heart Rate Reserve

RHR: Resting Heart Rate

MHR: Maximum Heart Rate

THRX%: Target heart rate to be at X% of HRR

Smoking code: "1" if the subject is a smoker and "0" if the subject is not a smoker

Equation 1 provides the MHR for men. The Target Heart Rate is provided by equation 3.

$$\text{MHR} = 203.9 - (0.812 \times \text{Age}) + (0.276 \times \text{RHR}) - (0.084 \times \text{Weight}_{\text{kg}}) - (4.5 \times \text{smoking code}) \quad (1)$$

Equation 2 provides the MHR for women.

$$\text{MHR} = 204.8 - (0.718 \times \text{Age}) + (0.162 \times \text{RHR}) - (0.105 \times \text{Weight}_{\text{kg}}) - (6.2 \times \text{smoking code}) \quad (2)$$

Target Heart Rate for exercise (at 50%) is provided by equation 3:

$$\text{THR}_{50\%} = [(\text{MHR} - \text{RHR}) \times 50\%] + \text{RHR} \quad (3)$$

References:

Whaley MH, et al, *Predictors of over- and underachievement of age-predicted maximal heart rate*, Med Sci Sports Exerc 1992;24(10):1173-9;  
[Karvonen MJ](#), [Kentala E](#), [Mustala O](#). The effects of training on heart rate; a longitudinal study. [Ann Med Exp Biol Fenn](#). 1957;35(3):307-15;  

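### At the stated clock times the 5-hour breakfast window includes about an hour of exercise and recovery, and the dinner window includes none

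*Combined protocol and SAP*

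**What the plan says.** Section 16.3, Table 16-2 lists among the primary measures the percentage "of time within zone [70-180] mg/dL 5 hours after unannounced evening meal, and breakfast". Both meals share that row, which is described as showing how the device reacts to a small meal. Table 16-3 adds a 0-5 h post-meal mean and an AUC per gram of carbohydrate over 5 hours. The Executive Summary adds glucose at 1 and 2 hours and a 6-hour AUC.

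On timing, the synopsis says "Another small meal (~50 g CHO) will be given for breakfast at approximately 7:00 am" and "At 11:00 am, the subject will be given a snack (~16 g CHO) and start exercise". Sections 10.1, 10.4.3.2 and 10.4.3.3 give the same clock times. Section 10.4.4 instead places exercise "Approximately 5 hours after the breakfast (11:00 am", give or take 30 minutes. The bout is "15 minutes of exercise, 5-minute break, followed by 15 additional minutes of exercise".

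Whether and when a subject exercises depends on glucose. Above 270 mg/dL "the subject will not go through the exercising segment of the trial". A subject below 120 mg/dL receives 16 g of carbohydrate and "will not start exercise until glucose is greater than 120 mg/dL".

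Section 16.1 removes the post-meal and exercise periods from the [80-140] mg/dL measure. It gives no rule for the time when those periods overlap each other.

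**The concern.** If exercise starts 4 hours after breakfast, the last hour of the 5-hour breakfast window is an exercise challenge and not only a meal response. Dinner has no such hour. Section 3.3.4 raises breakfast to 50 g so that it matches dinner, so a reader will naturally set the two percentages side by side.

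Three features make this more than a fixed offset:

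- **The overlap depends on glucose.** Exercise is delayed or skipped according to the subject's own glucose about 4 hours after breakfast, so what hour 5 contains varies between subjects and is related to the outcome.
- **Extra carbohydrate falls in the same hour, and the documents disagree on it.** The synopsis gives the pre-exercise snack without a condition and Section 10.4.3 lists it without one. Section 10.1 has "At 11:00 am, a small snack of approximately 16 g CHO if YSI value is" below 120 mg/dL, and Section 10.4.3.3 has the same condition.
- **The hour is scored twice.** It counts against [70-180] as post-breakfast time and against [70-150] as exercise or post-exercise time. A reading of 165 mg/dL is in range in one row of Table 16-2 and out of range in another.

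**Working it through.** **Inputs.** Breakfast 7:00 and exercise 11:00 (synopsis; Sections 10.1, 10.4.3.2, 10.4.3.3, 10.4.4). Dinner 18:30 (Section 10.4.3.1). All times ±30 min (synopsis). One CGM reading every 5 min (Section 1.2). Bout of 15 + 5 + 15 = 35 min elapsed, or 30 min without the break (Section 10.4.4).

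**The plan's own figure.** Section 10.4.4 gives a gap of about 5 hours. The clock times give 11:00 − 7:00 = 240 min = 4 h, so the stated interval is not reproduced. With ±30 min on each time the gap runs from 10:30 − 7:30 = 180 min to 11:30 − 6:30 = 300 min. Five hours is reached only when breakfast is 30 min early and exercise 30 min late. Section 10.4.3.4 puts 3 h after exercise start at 2:00 pm, which gives 11:00. This does not settle which statement is intended.

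**Overlap.** Minutes of a breakfast window at or after exercise start = max(0, window − gap):

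| Window from breakfast | Readings | Gap 240 min (clock times) | Gap 180-300 min (tolerances) | Gap 300 min (Section 10.4.4) |
|---|---|---|---|---|
| 0-3 h (180 min) | 36 | 0 | 0 | 0 |
| 0-4 h (240 min) | 48 | 0 | 0-60 (at most 25%) | 0 |
| 0-5 h (300 min) | 60 | 60 (20%) | 0-120 | 0 |
| 0-6 h (360 min) | 72 | 120 (33%) | 60-180 | 60 (17%) |

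If exercise is skipped, or starts after the window ends, the overlap is 0 in every row. At the clock times hour 5 holds the whole bout plus 60 − 35 = 25 min of recovery (30 min if the break is not counted). The dinner window, 18:30 to 23:30, holds no exercise at any tolerance.

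**Typical overlap.** Assume both times are spread evenly over ±30 min, with no skips or delays. The deviation of the gap from 240 min is then triangular on ±60 min.

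- 0-3 h: 0 min.
- 0-4 h: mean 60 × ∫₀¹ t(1 − t) dt = 60/6 = 10 min of 240 (4%), and half of subjects have some overlap.
- 0-5 h: mean 60 min of 300 (20%).
- 0-6 h: mean 120 min of 360 (33%).

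**Leverage on time in range.** At the clock times, 5-h percentage = 0.8 × (hours 0-4) + 0.2 × (hour 5). Each 10 points by which hour 5 differs from hours 0-4 moves the 5-hour figure by 0.2 × 10 = 2 points, in either direction.

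**Scale of the snack.** 16 g against a 50 g meal: 16/50 = 32%.

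**Measures not affected.** The 1-hour and 2-hour values precede exercise even at the minimum gap of 3 hours.

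**The case against.** The arithmetic is hard to dispute, so the case against is about importance and remedy.

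- **No planned inference is shown to be harmed.** Section 14 says the goal is feasibility and not efficacy. Section 12 gives 12 to 20 subjects, and no dinner-versus-breakfast test is specified. The planned comparison is with G110093 in subjects enrolled in both studies. Section 3.3.4 says the design is otherwise unchanged apart from the inhaled dose and breakfast size, so the overlap is largely shared.
- **The meals may well be reported separately.** Table 3-1 for the earlier study lists dinner (72%) and breakfast (63%) in separate columns. The 63-72% range in the text restates those two figures and does not show pooling.
- **A shorter window removes only one difference between the meals.** Dinner comes about 2 h into closed loop and breakfast about 14.5 h in, after a night.
- **The 0-4 h window is not fully clean,** and zero exercise overlap does not mean an undisturbed window, because a subject below 120 mg/dL may receive carbohydrate while exercise is delayed.

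Much of this stands as a limit. No test is invalidated, the size of any effect is unknown, and the meals would remain imperfectly comparable. But in a descriptive study the reported percentages are the result, and separate columns do not remove exercise from the breakfast one. Nothing in the plan warns the reader. The residual overlap in 0-4 h is the reason for a 0-3 h sensitivity window, and the carbohydrate point is the reason to count intake inside the window. The 1-hour and 2-hour values are unaffected, but they are point values and do not replace time in range, mean or AUC.

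**Conclusion.** The concern holds. At the stated clock times one fifth of the 5-hour breakfast window, and one third of the 6-hour breakfast AUC, lies at or after the start of exercise, against none for dinner. The plan neither handles nor mentions this. The 5-hour overlap ranges from 0 to 120 minutes within the tolerances. It is zero if exercise is skipped, is delayed beyond the window, or starts 5 hours after breakfast as Section 10.4.4 states.

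The conclusion rests on the 7:00 and 11:00 clock times. The two timeline figures (10-2 and 10-3) could not be seen. No direction or size of bias is claimed. The consequence is that a primary measure described as the reaction to a small meal cannot be read as that for breakfast. It should be fixed before analysis, and doing so is cheap.

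**What to change.** 1. Keep the 0-5 h and 6-h figures for both meals, for comparison with G110093, and label the breakfast ones as including exercise and recovery.
2. Add a fixed 0-4 h window for both meals: time in [70-180] mg/dL, mean glucose and AUC.
3. Report the same three measures over a fixed 0-3 h window as a sensitivity analysis, since it is free of exercise across the whole ±30 min tolerance.
4. Do not cut any window at the actual start of exercise, because that time depends on glucose.
5. Report how many subjects exercised, and how many took carbohydrate, inside the 5-hour breakfast window.
6. Reconcile the interval in Section 10.4.4 with the clock times. Reconcile the pre-exercise snack statements in the synopsis and Section 10.4.3 with those in Sections 10.1 and 10.4.3.3.

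The cost is SAP wording, 3 measures × 2 meals × 2 windows = 12 descriptive figures, and two counts. The meal and exercise time stamps are already collected (Section 17.1). The downside is that the shorter windows may give a lower breakfast percentage, because they leave out a late and possibly recovered part of the meal response.

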#### Guiding questions:

- (1) Did the algorithm deliver insulin in a pattern conducive to causing or maintaining within-zone CGM measurements?
- (2) Did the algorithm deliver reasonable size insulin amounts? Did the algorithm deliver the basal amount of insulin in quiescent, within-zone period? When CGM measurements were predicting values higher than the upper zone limit of [80-140] mg/dL, did the algorithm increase insulin infusion? When CGM measurements predicted values lower than the lower zone limit of [80-140] mg/dL, did the algorithm decrease insulin infusion? After glucose excursion above the upper zone limit or below the lower zone limit, when the CGM

measurements predicted measurement was reentering the zone, did the algorithm resume the basal amount of insulin infusion?

- (3) When prediction of BG glucose was to be <70 mg/dL in the following 15 minutes, did the HMS send a warning text to physician? Did the HMS system send unnecessary warning text messages when the BG was not predicted to be <70 mg/dL? Did the investigator need to give CHO to the subject without receiving notification from the HMS either because of CGM failure or HMS system failure?

## 16.4. Secondary end-points

### 16.4.1. Analyses

In addition to the qualitative evaluation of the performance of the AP device, the percentage of time spent in each zone, and the visual evaluation provided by CVGA plots, other quantitative measures will be reported, analyzed and interpreted. They are presented in [Table 16–3](#). Unless indicated otherwise, the calculations are performed using CGM values.

**Table 16–3: Secondary end-points measures**

Measure	Description
Averages	
Mean glucose level during the 24-hour closed-loop	Computed from CGM and then YSI values
Mean-pre meal glucose value	Computed 0-60 minutes before unannounced evening and morning meal
Mean-post meal glucose value	Computed 0-5 hrs after the evening and morning meal
Mean exercise glucose value	Computed value during the 30 min of exercise
Mean-pre-exercise glucose value	Computed 0-60 minutes before exercise
Mean-post exercise glucose value	Computed 0-3 hrs after end of exercise
Extremes	
% of time of glucose > 400 mg/dL	Computed from CGM and YSI values: analysis during 24 hour closed-loop, during night (12:00 am to 7:00 am) and during exercise
% of time of glucose ≥ 300 mg/dL	Computed from CGM and YSI values if duration is more than 1 hour: analysis during 24 hour closed-loop, during night (12:00 am to 7:00 am) and during exercise
% of time of glucose < 60 mg/dL	Computed from CGM and YSI values: analysis during 24 hour closed-loop, during night (12:00 am to 7:00 am) and during exercise
% of time of glucose ≤ 70 mg/dL	Computed from CGM and YSI values if duration is more than 1 hour: analysis during 24 hour closed-loop, during night (12:00 am to 7:00 am) and during exercise
Area under the curve per gram CHO	Computed from the beginning of a meal and continued for 5

Measure	Description
	hours
Area under the curve during exercise	Computed during exercise and for 3 hours following exercise
Area between the curve and nearest zone limit when outside the range [80-140] mg/dL	This will measure how much deviation from the zone. The analysis may be performed for the 24-hour closed-loop, for the night (12:00 am to 7:00 am), and during/following exercise and meals.
Total amount of insulin delivered and standard deviation of delivery amounts during the 24-hour closed-loop	Correspondence of total insulin delivered to total daily insulin (TDI)
Variability and risk assessment (*)	
Interquartile range	It measures the spread around the center of the desired zone, i.e. 110 mg/dL
LBGI: Low blood glucose index	Measures the frequency and extend of low blood glucose readings using CGM data
HBGI: High blood glucose index	Measures the frequency and extend of high blood glucose readings using CGM data
Blood glucose index: LBGI+HBGI	Measure the overall variability and the associated risk with hypoglycemia and hyperglycemia.
Standard deviation of glucose rate of change	Measures the stability of the closed-loop over time

(\*) See details of calculations in section [16.4.2+10.4.2](#).

The review of the secondary end-points will also include the review of all AEs, SAEs, UADE, and complaints. It will also include the review of the need of outside intervention to safely manage the subject.

Data will be presented in table or graphs or both. Data of all subjects may be pooled together or may be presented individually. Should it be warranted, data may also be pooled in different sub-groups.

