Study Purpose	
Primary objective of this feasibility study:                      To evaluate the performance of the AP device while the subject is under close medical supervision in the Clinical Research Center (CRC) setting.
 
This objective will be assessed by subjecting the AP device (combined with the Technosphere® Insulin Inhalation Powder) and the subject to several challenging situations, such as meals, exercise, and nocturnal period. The study will evaluate the percent of time the glucose level of the subject remains within pre-specified target ranges:
 
 
• Target range (unless described otherwise): [80-140] mg/dL
 
• Overnight target range: [80-140] mg/dL
 
• Target range 5 hours after meal: [70-180] mg/dL
 
• Target range during exercise: [70-150] mg/dL
 
• Target range 3 hours after exercise: [70-150] mg/dL
 
 
The study will also evaluate the glucose level at 1- and 2-hour postprandial and the area-under-the-curve (AUC) at 6-hour post-prandial.
 
Secondary objectives:                      To evaluate the performance of the AP device combined with the Technosphere® Insulin Powder System:
 
 
• when glucose values are outside of the desirable ranges,
 
• in analyzing the values and duration of the extremes, in particular if <70 mg/dL and <60 mg/dL.
 
• in analyzing adverse events,
 
• in analyzing outside interventions not following the recommendation of the HMS,
 
• if the same subjects were enrolled in this study and the original IDE G110093 study (protocol revision 2.2): comparing the glucose profile between the two clinical studies with and without the Technosphere® Insulin.
 

Study Design	Non-randomized, uncontrolled, feasibility study conducted in the United-States at one clinical site, with one principal investigator.  Overview of the procedures:

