--	--

	
collect information, but no decision will be made from the results of the finger stick.
 
If the HMS recommends giving CHO to the subject, the investigator will follow the recommendation. Any other outside intervention by the investigator will terminate the study session for that subject. If clinical results from a subject are found to be suboptimal with excessive hyperglycemia or excessive hypoglycemia alarms, the responsiveness factor of the control algorithm may be adjusted for the study of the next subject.
 
Once the glucose level of the patient is back to more than 90 mg/dL for more than 1 hour, and the glucose level is less than 180 mg/dL with ketones less than 0.6 mmol/L, the patient will be discharged from the CRC.
 
On the day following the CRC visit, the study staff will be in contact, by telephone or in person with the subject for follow-up.

Subject Population	
Adults aged 21-65 years                      Type 1 diabetes mellitus for at least one year                      Using an insulin infusion pump with rapid acting insulin for at least six months

Sample Size	12 to 20 subjects
Duration of the subject participation	Total duration by each subject is expected to be approximately one week from time of contact to review glucose control to follow-up after discharge from CRC visit.
Study Center	Sansum Diabetes Research Institute, Santa Barbara, CA

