#### **1.4. Control algorithm**

The control algorithm is unique to this application: it combines a zone-Model Predictive Control (MPC) algorithm with the added safety feature of the Health Monitoring System (HMS) which provides warnings and notifications of impending hypoglycemia to request outside intervention, such as absorption of fast acting glucose. The notification is not only available to the subject via the AP device, but also to the physician or another person who could be located remotely in the future (this IDE exclusively takes place in the clinical research setting in presence of a physician). The HMS algorithm uses the same CGM data as the zone-MPC control algorithm but utilizes a separate algorithm for trending and predictions of future glucose values. Using a redundant and independent algorithm is an important safety feature of the overall AP device. The HMS will send a warning to the AP device and a text message to the attending physician (present at all times) whenever it predicts a glucose value below 70 mg/dL within the next 15 minutes. The warning will include a recommendation to give the subject approximately 16 g of carbohydrates. The warning must be acknowledged for the pop-up window to close. The acknowledgement gives the choice to “accept” or “ignore” the warning and recommendation.

The zone-MPC control algorithm is at its core a Model Predictive Control (MPC), which incorporates an explicit model of human T1DM glucose-insulin dynamics. The model is used to predict future glucose values and to calculate future controller moves that will bring the glucose profile into the desired range. Software constraints ensure that insulin delivery rates are constrained between minimum and maximum values. The first insulin infusion (out of  $n$  steps) is then implemented. At the next time step,  $k + 1$ , the process is repeated based on the new measured glucose value and the last insulin rate. The algorithm adjusts insulin delivery automatically to achieve and maintain the patient’s glucose level within a predetermined safe range: 80-140 mg/dL. The only variable that may be adjusted between subjects is the *responsiveness factor* which is the ration of  $Q/R$ . It can be described as the agility of the control algorithm to respond to

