## **2.2. Primary and secondary endpoints**

The assessment of the performance of the device will be based principally on two types of metrics:

- Primary endpoints: percentage of time spent within a specific zone, in particular the desired zone [80-140] mg/dL. Other zones will be defined after meal or exercises.
- Secondary endpoints: review of the extremes of the glucose values of the subject, duration of those extremes and the review of any event requiring outside intervention to treat hypoglycemia or hyperglycemia.

**The primary endpoint** of the clinical study is the amount of time spent within a specified glucose target range. In this study there will be different ranges depending on both time of day and time after meals and exercise:

- Target range (unless described otherwise): [80-140] mg/dL
- Overnight target range: [80-140] mg/dL
- 5 hours postprandial target range: [70-180] mg/dL
- During exercise: [70-150] mg/dL
- 3 hours post-exercise: [70-150] mg/dL

**The secondary endpoints** of the clinical study include excursions outside the range, the maximum value of the excursion, the duration the subject remains outside of the target ranges and whether or not there is any outside intervention to treat hypo- or hyperglycemia. The extremes are defined as follows:

- For hyperglycemia: any blood glucose value >400 mg/dL (measured by YSI)
- For hypoglycemia: any blood glucose value <60 mg/dL (measured by YSI)

In addition, a secondary end-point will consist in analyzing CGM values that were trending beyond the desirable ranges. The analysis will determine the percent of time spent in the following zones:

- If glucose value per CGM is  $\geq 300$  mg/dL for more than 1 hour;
- If glucose value is predicted to be  $\leq 70$  mg/dL by CGM ;
- If glucose value per CGM is  $\leq 70$  mg/dL;
- If glucose value per CGM is  $\leq 60$  mg/dL;

The secondary endpoints will also be assessed by evaluating all safety events.

The levels of hypoglycemia and hypoglycemia are described by [Table 15-2](#)~~Table 9-2~~.

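### Table 16-3 counts time at or below 70 mg/dL only when it lasts over an hour, so the row omits short lows and can fall below the <60 mg/dL row it should contain

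*Combined protocol and SAP*

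**What the plan says.** Among the extremes in Table 16-3 (Section 16.4.1) is the percentage "of time of glucose ≤ 70 mg/dL". Its definition reads "Computed from CGM and YSI values if duration is more than 1 hour: analysis during 24 hour closed-loop, during night", and the row is also analysed during exercise. The ≥300 mg/dL row has the same wording. The adjacent percentage, "of time of glucose < 60 mg/dL", uses CGM and YSI over the same three windows without a duration condition, as does the >400 row.

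Section 2.2 introduces its own list with "The analysis will determine the percent of time spent in the following zones". The list covers CGM ≥300, predicted ≤70, ≤70 and ≤60 mg/dL. Only the ≥300 entry is qualified by "mg/dL for more than 1 hour".

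The synopsis sets a secondary objective of evaluating performance "in analyzing the values and duration of the extremes, in particular if" below 70 and below 60 mg/dL, with no minimum duration.

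Two further passages bear on how long lows are likely to last. Under Section 1.4 the HMS issues a warning "whenever it predicts a glucose value below 70 mg/dL within the next 15 minutes", and the synopsis adds "If the HMS recommends giving CHO to the subject, the investigator will follow the recommendation".

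**The concern.** Section 2.2 and Table 16-3 define the same quantity differently, and an analyst working on this row cannot satisfy both. Nothing in the documents explains an hour's threshold for lows. For ≥300 mg/dL, by contrast, the hour appears consistently in Section 2.2, Table 16-3 and the safety actions of Table 10-2. The identical wording suggests a carry-over from the ≥300 row, though the documents do not say so.

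Within Table 16-3 this is the only direct time measure that includes the 60–70 mg/dL band. The unconditioned ≤70 zone in Section 2.2 is CGM only, so no other listed measure gives YSI time at or below 70. Adverse event records do not fill the gap: Table 15-2 grades values between 60 and 70 as negligible, and Section 15.2.5 documents only moderate or worse events on a CRF.

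The error runs one way. It makes the system's low-glucose record look better than it is.

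**Working it through.** The plan gives no figure for this row, so there is nothing to reproduce. The check compares the definitions and works through what they return.

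**1. Nesting.** Every minute below 60 is also a minute at or below 70, so the ≤70 percentage should never be the smaller. Take 24 h = 1,440 min, night (midnight to 7 am) = 420 min and CGM readings every 5 min. The cases below are illustrative, not trial data.

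| Low in one subject | True ≤70, 24 h | ≤70 row, hour per episode | ≤70 row, hour cumulative | <60 row |
|---|---|---|---|---|
| 30 min, all <60 | 30/1440 = 2.1% | 0% | 0% | 2.1% |
| 45 min, 15 min <60 | 45/1440 = 3.1% | 0% | 0% | 15/1440 = 1.0% |
| 60 min, 30 min <60 | 60/1440 = 4.2% | 0% | 0% | 2.1% |
| 65 min, 30 min <60 | 65/1440 = 4.5% | 4.5% | 4.5% | 2.1% |
| two of 45 min, 30 min <60 in total | 90/1440 = 6.25% | 0% | 6.25% | 2.1% |

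The plan does not say whether the hour is one continuous episode or cumulative time. The single-episode reversals occur under both readings. If the 30-minute low is nocturnal, the <60 row shows 30/420 = 7.1% of the night and the ≤70 row 0%.

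**2. Exercise window.** Section 10.4.4 gives 15 + 5 + 15 = 35 min with the break, or about 40 min with the 5-minute tolerance. More than 60 minutes cannot fit, so the exercise result is 0% by construction unless time outside the window counts toward duration.

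**3. Scale from the predecessor study.** Table 3-1 gives 1% of the whole closed loop below 70 by YSI, for 12 subjects. Assuming 24 h each:

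- Per subject: 0.01 × 1440 = 14.4 min (7.2 to 21.6 min for a true value of 0.5% to 1.5%).
- All 12 subjects: 172.8 min (86.4 to 259.2).
- A non-zero row needs more than 60 low minutes in one subject under either reading. The maximum number of such subjects is floor(172.8/60) = 2, or floor(259.2/60) = 4 at the rounding limit.
- So at least 10 (8) of 12 subjects would show 0% whatever low time they had.

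**4. Share of low time dropped.** This depends on episode lengths, which are not given. On the per-episode reading it runs from 0% (all low time in one or two long episodes) to 100% (every episode 60 min or less). As an assumption only, if lengths are exponential with mean m, the share of time in episodes over 60 min is (1 + 60/m)·exp(−60/m):

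- m = 15: 0.092 kept, 91% dropped
- m = 20: 0.199 kept, 80% dropped
- m = 30: 0.406 kept, 59% dropped
- m = 60: 0.736 kept, 26% dropped

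Carbohydrate is given on a predicted value below 70, so short lows are the kind to expect.

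**5. Comparability.** In Table 3-1 the <70, 70–180 and >180 percentages sum to 100% in seven of eight columns and to 99% in the other, as rounding allows. The predecessor's low-glucose time was therefore unfiltered, and a filtered row cannot be set beside it.

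**The case against.** The best counter-argument is that unconditioned CGM time at or below 70 is already promised in Section 2.2. Section 16.4.1 presents Table 16-3 as an addition to the time-in-zone results, so the row could be read as a deliberate measure of prolonged lows with a poor label. That reading is available, but the row is not labelled as such and Section 16.4.1 does not refer to the Section 2.2 list. Even then, YSI time at or below 70 is specified nowhere else.

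A second objection is that the ≥300 row has the same condition beside an unconditioned, nested >400 row, so nesting alone cannot single out ≤70. That is true. What distinguishes the ≤70 row is that its condition contradicts Section 2.2, whereas the ≥300 condition is stated consistently.

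Other points stand as limits:

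- The exponential shares rest on an assumed distribution and apply only to the per-episode reading.
- Table 3-1 is YSI below 70, from a study without pre-meal inhaled insulin.
- Table 3-1 shows 0% below 70 overnight and during exercise, so at that rate the loss falls in the rest of the 24 hours.
- The row is descriptive, with no test or decision rule attached. The <60 row, LBGI, the area outside 80–140 mg/dL and the review of HMS warnings still reflect lows.

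**Conclusion.** The concern holds. The one-hour condition on the ≤70 row conflicts with Section 2.2, biases the reported low time toward zero, and allows a result below the <60 row under either meaning of duration. The contradiction and the reversal follow from the text alone. The estimate that at most 2 of 12 subjects (4 at the rounding limit) could be non-zero assumes the predecessor's YSI rate and 24 hours per subject. The proportion of low time lost cannot be fixed from the documents. This should be corrected, but it affects one secondary descriptive row and no inferential result.

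**What to change.** Delete the one-hour condition from the ≤70 mg/dL row of Table 16-3 and report all time at or below 70, by CGM and by YSI, for 24 hours, night and exercise. That removes the conflict with Section 2.2 over duration and restores the ordering against the <60 row. The ≥300 row can stay as it is.

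If prolonged lows are of interest, add a separately labelled count of ≤70 episodes longer than one hour. State how an episode starts and ends, and how one that crosses a window boundary is counted. While editing, note that Section 2.2 uses ≤60 by CGM and Table 16-3 uses <60 by CGM and YSI; this smaller mismatch is not cured by the deletion.

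The cost is one line of analysis wording. No new data are needed and no treatment rule changes. The reported low-glucose time may be less favourable.
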